11.3 Exploratory Efficacy Analyses

An interaction term between treatment and the fixed effect covariates will be added to the primary efficacy model. Predicted probabilities for diagnostic risk with 95% confidence intervals will be shown for subgroups/covariates in case of any statistically significant interactions ($p < 0.05$). Additionally, interactions will also be performed for the analyses on the individual parameters of the composite primary endpoint score.

Additional exploratory analyses for secondary efficacy analyses or other endpoints may be conducted as appropriate. Any additional exploratory analyses will be appropriately labeled and clearly distinguished from planned analyses when results are reported in the clinical study report.

12 Safety Analyses

Serious adverse event incidences will be described using counts and proportions for each event category and treatment group (intervention and control). Each subject will only be counted once and any repetitions of serious adverse events will be ignored; the denominator will be the population size of the respective group. If multiple serious adverse event categories are checked for one single event, the event will be assigned to one category only in following order: Death; life-threatening illness or injury; permanent disability / incapacity; medical or surgical intervention to prevent life-threatening illness, injury or permanent impairment; Congenital anomaly / birth defect; Chronic disease; Hospitalization or prolongation of existing hospitalization.

(Serious) Adverse Events will be listed and described if a relation with the clinical investigational protocol or the medical device under investigation cannot be excluded.

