9.3 Covariates and Subgroups

Subgroup analyses and treatment interactions will be assessed with following covariates/subgroups:

- Patient characteristics (Age, sex, chief complaint)
- Disease characteristics: confidence, difficulty, familiarity, typicality
- Physician characteristics: medical experience, emergency experience, medical specialist

All analyses on interactions and subgroups are explorative and described in section 11.3 or 13.

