10.6 Treatment Compliance

Number of queries and the average number of symptoms entered into the DDx generator per patient will be used for treatment compliance. In addition, self-reported usage of CDDS outside the study protocol [othercdds1] will be reported.

11 Efficacy Analyses

Data will be summarized by treatment groups. N, mean and standard deviation will summarize continuous efficacy variables, whereas number and percent will summarize categorical efficacy variables. Statistical analyses will be based on multi-level general linear mixed modelling (GLMM) methods using appropriate post hoc techniques (e.g for subgroup analyses). Regression coefficients for continuous endpoints and odds ratios for binary endpoints and geometric mean ratios for ln-transformed continuous outcomes will be displayed as measure of strength accompanied by their 95% confidence intervals. Viewing plots along with normality testing (e.g. Shapiro-Wilk) will be used in order to check assumptions for the appropriate use of parametric testing approaches. Transformations to normality for variables not fulfilling normality assumptions will be considered (e.g. log, Box-Cox etc.), while nonparametric testing using counterparts of ad-hoc parametric procedures will also be an option as needed (e.g. Kruskal-Wallis instead of one-way ANOVA, the latter being part of the GLM family). R (R Foundation for Statistical Computing, Vienna, Austria) will be used for data analysis. A test-wise 2-sided p-value of less than 0.05 will be considered statistically significant.

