11.1 Primary Efficacy Analysis

For the primary binary outcome, presence or no presence of a diagnostic quality risk, a generalized linear mixed model (GLMM) with a binomial distribution family and exchangeable correlation structure will be performed. The GLMM takes into account a random intercept for each site, resident and attending physician. In some cases, patients may be treated by more than one resident or attending physician due to changes in shift. The physicians who were initially involved in treatment will be selected as diagnosing physicians. The condition (intervention and control) and the period (period 1 to 6) will be included as fixed factors under the assumption of equality of carry-over effects. Additionally, chief complaint, age, sex and Charlson Comorbidity Index will be added as covariates. The primary efficacy analysis will be performed on the ITT set.

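### Subgroup predictions for the composite endpoint are to be shown only if the interaction reaches p<0.05, and nothing commits the authors to report the other interactions or how many were tested

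*SAP*

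**What the plan says.** Four parts of the SAP bear on this.

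- **11.3 (what is tested).** "An interaction term between treatment and the fixed effect covariates will be added to the primary efficacy model". Interactions are also planned for each component of the composite.
- **11.3 (what is shown).** "Predicted probabilities for diagnostic risk with 95% confidence intervals" are to be shown by subgroup or covariate "in case of any statistically significant interactions", with p<0.05 given as the threshold. The component interactions come in the next sentence, which has no display rule.
- **9.3 (which modifiers).** "Subgroup analyses and treatment interactions will be assessed with following covariates/subgroups". The list has ten variables: age, sex and chief complaint; confidence, difficulty, familiarity and typicality; medical experience, emergency experience and specialist status. The section calls all these analyses explorative and refers to 11.3 or 13 for their description.
- **9.6 and the opening text of 11 (error rate).** No adjustment for multiplicity is planned, and the issue is left to the limitations section of the papers. "A test-wise 2-sided p-value of less than 0.05 will be considered statistically significant".

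On output, Table 2 (18.3) has no row for an interaction. Figure 2 (18.5) says only that exploratory analyses may be presented as interaction plots.

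**The concern.** A display rule that depends on the p-value selects on the size of the estimate. The interactions that appear with subgroup predictions are those that happened to be large in this sample. Readers who see them without the flat ones cannot judge how surprising they are. The explorative label and a sentence on multiplicity do not cure this, because neither shows the rest of the results nor shrinks the estimates that passed.

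The number of tests is also not fixed. SAP 11.3 refers to the fixed-effect covariates of the primary model, and 11.1 says "chief complaint, age, sex and Charlson Comorbidity Index will be added as covariates", with period as a further fixed factor. The list in 9.3 omits the Charlson index and adds seven physician-rated and physician variables. Section 13 describes no treatment interaction that would place those seven elsewhere. If only significant results must be displayed, a reader of the paper may be unable to recover how many tests were made.

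**Working it through.** The SAP gives no count of interaction tests and no error rate for them. Its sample size is checked first, because the exaggeration calculation uses it.

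**1. Planned size (SAP 8).** Inputs: 12% against 7% (a difference of 5 points), 80% power, two-sided 0.05, intra-cluster correlation (ICC) 0.01, 10% loss.
- Per condition: [1.96 × √(2 × 0.095 × 0.905) + 0.8416 × √(0.12 × 0.88 + 0.07 × 0.93)]² / 0.05² = 539.
- Total for a balanced multi-period cross-over with exchangeable correlation: 2 × 539 × (1 − 0.01) / 0.9 = 1186, against the stated 1184. The figure reproduces.
- Evaluable patients: 1184 × 0.9 ≈ 1066, or 533 per condition.

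**2. Tests on the composite.** Each modifier is counted as one test, including chief complaint with its four levels.
- Covariates in 11.1: 4, or 5 with period.
- The 9.3 list: 10. Adding the Charlson index gives 11, and adding period gives 12.

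**3. False positives if no interaction exists.** Expected number = 0.05k. Chance of at least one, if independent = 1 − 0.95^k.

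| k | Expected | At least one |
|---|---|---|
| 4 | 0.20 | 0.19 |
| 5 | 0.25 | 0.23 |
| 10 | 0.50 | 0.40 |
| 12 | 0.60 | 0.46 |

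**4. What passes the filter.** Assume a two-level subgroup and a normal approximation on the log-odds scale, ignoring clustering.
- SE of the main log odds ratio: √[1/(533 × 0.12 × 0.88) + 1/(533 × 0.07 × 0.93)] = 0.216.
- SE of the interaction with shares s and 1 − s: 0.216 / √(s(1 − s)). This is 0.432 at 50:50 and 0.471 at 30:70.
- Smallest ratio of odds ratios shown: exp(1.96 × 0.432) = 2.33 (or 0.43 in the other direction). At 30:70 it is 2.52 (or 0.40).

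The mean absolute log ratio among shown results comes from simulation of that normal distribution (2,000,000 draws). At 50:50:

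| True ratio | Chance shown | Mean absolute log ratio if shown | Overstatement of log ratio |
|---|---|---|---|
| 1.00 | 0.05 | 1.01 (ratio 2.75) | – |
| 1.35 | 0.11 | 1.05 (ratio 2.85) | 3.5-fold |
| 1.81 | 0.28 | 1.11 (ratio 3.04) | 1.9-fold |

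A ratio of 1.81 is as large as the planned main effect: the odds ratio for 7% against 12% is 0.55, and 1/0.55 ≈ 1.81. A ratio of 1.35 is half that on the log scale. At 30:70 the two overstatement factors are 3.8 and 2.0.

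**The case against.** The strongest reply is that the rule governs one display and suppresses nothing. The opening text of section 11 says that odds ratios for binary endpoints will be displayed with 95% confidence intervals, without a significance condition. On that reading, interaction estimates are reported anyway, and predicted probabilities are an extra aid where an interaction is found. Section 18 allows further supplementary tables and figures. The modifiers are listed in advance, the analyses are declared explorative, and multiplicity is to be discussed as a limitation.

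Much of this stands. A reader might infer that non-significant subgroups will be withheld, but the SAP never says so. A reader might also multiply ten variables by five endpoints and arrive at 50 tests, 2.5 expected false positives and a 92% chance of at least one. The text does not support applying that to this rule. The sentence names diagnostic risk, which is the composite in 10.2, and no display rule is set for the components. The components are also dependent on the composite by construction, so an independence figure across all five would be too high. Nor does 9.3 place all ten variables under 11.3.

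The general line on odds ratios does not close the gap. It does not mention interactions, no planned table has a place for them, and the interaction plots are optional. The explorative label answers a demand for alpha adjustment, which is not made here; it does not answer selective display.

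**Conclusion.** The point holds as a reporting weakness in the exploratory analyses. One pre-specified display for the composite is filtered on p<0.05, and complete reporting of the interactions is neither promised nor ruled out. Its size is 4 to 12 tests, 0.2 to 0.6 expected false positives, and a 19% to 46% chance of at least one. These figures assume no true interactions. The upper end needs the 9.3 list to be added to the primary-model covariates. The chance of at least one also assumes independence; correlation between tests would not change the expected counts.

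The exaggeration factors rest on assumed 50:50 and 30:70 splits and ignore clustering, so they are indicative. Selection by a threshold inflates what is shown in any case, and at this sample size the inflation is likely to matter. The primary efficacy test is not affected.

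**What to change.** - In 11.3, delete the p<0.05 condition.
- Use one list of modifiers in 9.3 and 11.3, and state whether the Charlson index and period belong to it.
- Report every interaction tested, for the composite and the components, with estimate, 95% confidence interval and p-value, whatever its significance. State the number of tests. One supplementary table or forest plot is enough.
- Keep numeric modifiers (age, medical and emergency experience, Charlson index) continuous, or set cut-points in advance.
- Present confidence, difficulty, familiarity and typicality separately, and say that they are measured after the intervention. SAP 7.5.4 has them rated by the diagnosing physician at 0 to 3 days, and 7.3 says that treating physicians cannot be blinded, so the intervention may have influenced the ratings.

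The models are already planned, so the cost is one supplementary table or figure and a few sentences in the SAP. No alpha adjustment is needed. This is a cheap improvement.

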12.1 Other Safety Measures

The analyses of other safety endpoints as specified in 7.5.3 are described in 11.2.2.

13 Other Analyses

a) Validation of the diagnostic risk score

Fifty patients with a diagnostic risk (positive primary endpoint) and 50 patients without a diagnostic risk (negative primary endpoint) will be randomly selected among patients from three of four participating sites that share the same electronic health record system (Insel, Tiefenau, Muensingen). If there are less than 50 cases with a positive primary endpoint, the missing cases will be replaced with patients with a negative risk score. A random sampling function of the statistical software R will be used to determine the subset for the full chart review.

For the selected 100 patients, two independent investigators will rate their agreement on a 7-point likert scale for 13 questions regarding presence or absence of a diagnostic error using the revised Safer Dx instrument (3) Ratings between cases with positive and negative risk score will be compared using unpaired two-samples Wilcoxon test. Additionally, logistic regression models will be performed with the primary endpoint composite score as dependent variable and the rating score as independent variable. Additionally, following variables will be added as covariates: site, group allocation, period, site, patient's age, sex, chief complaint and Charlson comorbidity index.

b) Monitored CDDS usage

- Descriptive:
Average number of queries per patient and user and average number of entered symptoms per query and user will be summarized overall, for sites separately and over time using descriptive statistics and illustrating figures.
- Association with physician characteristics:
Physician characteristics physician characteristics (7.5.4) related to CDDS usage will be assessed with linear models. The average number of queries per patient and average entered symptoms per query will be calculated for each resident physician and used as dependent

variables. Phase, age, sex, medical experience, emergency experience, medical specialist and site will be added as independent predictors.

c) *Self-reported usefulness and impact of CDDS*

- Descriptive:

Counts and percentage will be used to describe the impact of the CDDS on diagnosis, confidence, diagnostics, consultations and general helpfulness (See 7.5.4).

- Association with physician and patient characteristics:

Logistic regression models for the binary endpoints described above will be performed. Physician related variables (age, sex, medical experience, emergency experience, medical specialist) and patient related variables (chief complaint, triage level, charlson-comorbidity index and length of ED stay) as well as site will be added as independent predictors. Predictor estimates will be and presented as Odds Ratios alongside 95% confidence intervals using Forest plots. Models will be repeated without physician related variables to explore the potential influence of missing values in physician related covariates.

d) *Number of cases where a generated DDx list entails the primary diagnosis after 14d*

ICD-10 Codes provided form the CDDS will be automatically compared with the ICD-10 Code of the primary diagnosis at follow-up using a batch tool.(8) Contingency tables for patients with and without change in diagnosis (diagnostic discrepancy) will be reported.

14 Reporting Conventions

P-values ≥ 0.001 will be reported to 3 decimal places; p-values less than 0.001 will be reported as " <0.001 ". Other statistics will be reported as integers or rounded to one or two decimal places as appropriate.

15 Quality Assurance of Statistical Programming

A second statistician will review and independently reproduce the primary analyses and summary statistics. The reviewing statistician will have an overview of the entire analyses and will explicitly check the code producing tables as well as any other pieces of code as desired.

16 Summary of Changes to the Protocol and/or SAP

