7.5.4 Covariates

Variables	Description	Scale	Time Window
Group allocation	control or intervention phase at time of inclusion	0, control phase 1, intervention phase	baseline
Phase	Number of phase at time of inclusion	Numeric, range 1-6	baseline
Age	Age in years	numeric	baseline
Sex	Sex	1, male 2, female	baseline
Chief complaint		0, fever 1, abdominal pain 2, syncope 3, non-specific complaint	
Triage level	Triage level	2-5	baseline
Admission type	Admission to the ED	0, Self-admittance 1, Ambulance 2, Air Rescue 88, other	baseline
Referral type	Type of referral to the ED	0, self-referral 1, GP 2, Hospital (intern) 3, Hospital (extern) 4, Air rescue (primary) 5, Ambulance (primary) 88, other	baseline
Charlson-Comorbidity-Index	Charlson Comorbidity Index (CCI) is Score of 19 comorbid conditions weighted from 1 to 6	Numeric, range 0-37	baseline
Confidence	Confidence regarding proposed primary diagnosis. (self-reported by the diagnosing physician via online survey)	Likert scale from 1 = not confident (50%) to 5 = confident (100%)	0-3 days
Difficulty	Perceived difficulty of the diagnostic reasoning process. (self-reported by the diagnosing physician via online survey)	Likert scale from 1 = difficult to 5 = easy	0-3 days
Familiarity	Familiarity/experience with the diagnosis (self-reported by the diagnosing physician via online survey)	Likert scale from 1 = not seen before to 5 = familiar	0-3 days
Typicality	Diagnosing physician judgement if the patient's presentation was atypical for the primary diagnosis.	0, typical 1, atypical	0-3 days
Diagnosing physicians	ED physicians (senior and resident) responsible for the treatment during patient's ED stay are recorded	Unique ID	length of ED stay, up to 24 hours
Age (physician)	Age in years	numeric	baseline
Sex (physician)	Sex of the diagnosing physician	1, male 2, female	baseline
Medical experience (physician)	Time of medical experience since obtaining the medical degree (years)	numeric	baseline
Emergency experience (physician)	Time of medical experience in emergency medicine (years)	numeric	baseline
Medical specialist (physician)	Medical specialist degree	0, no 1, yes	baseline

8 Sample Size

The sample size calculation has been performed for a multi-period cross-over cluster randomized controlled trial using according to Hemming at al. (2020) using the web-tool The Shiny CRT

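### The adjusted logistic model in the risk-score validation (SAP section 13 a) has 11 or 15 slopes for at most 50 positives, so ordinary maximum likelihood would overstate a real odds ratio

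*SAP*

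**What the plan says.** SAP section 13 a) fixes the sample by score status: "Fifty patients with a diagnostic risk (positive primary endpoint) and 50 patients without a diagnostic risk (negative primary endpoint) will be randomly selected". Charts come from three of the four sites. Fifty positives is a ceiling, because "If there are less than 50 cases with a positive primary endpoint, the missing cases will be replaced with patients with a negative risk score".

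Two analyses follow. The first is an unpaired Wilcoxon test of the ratings between score-positive and score-negative patients. The second is introduced as an addition: "logistic regression models will be performed with the primary endpoint composite score as dependent variable", with the rating score as the predictor. The covariates for it are "site, group allocation, period, site, patient's age, sex, chief complaint and Charlson comorbidity index", so site appears twice.

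The section does not say whether period enters as a factor or as a number. It also leaves open which item or summary of the 13-item instrument is the rating score, and how the two raters are combined. It names no penalisation. Planned Table 3 (section 18.4) shows item ratings with Wilcoxon p values and has no odds-ratio column.

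**The concern.** A maximum-likelihood logistic model with few cases per coefficient gives slopes that are too far from zero and intervals that are too narrow. Here the smaller outcome class has at most 50 members, and the covariate list closely follows that of the primary model, which was meant for a trial of more than 1,000 patients.

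The composite combines death, unscheduled care, unexpected ICU transfer and diagnostic discrepancy, yet it is read as a risk of reduced diagnostic quality. SAP section 7.3 gives validation of that measure as the purpose of the chart review. If the adjusted odds ratio is quoted as the strength of agreement between score and chart review, it will look stronger than it is.

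**Working it through.** **The plan's own figure.** The SAP gives no power, precision or cases-per-coefficient basis for the 50 + 50 charts, so there is no calculation to reproduce.

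**Slope count.**
- Rating: 1.
- Site: three sites (section 13 a), 2.
- Group allocation: 1.
- Period: 5 if a factor, as in the primary model (section 11.1); 1 if numeric, as Phase is coded in section 7.5.4.
- Age 1, sex 1, Charlson index 1.
- Chief complaint: four levels (section 7.5.4, "0, fever 1, abdominal pain 2, syncope 3, non-specific complaint"), 3.

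Period as factor: 1 + 2 + 1 + 5 + 1 + 1 + 1 + 3 = 15, so 50/15 = 3.3 positives per slope. Period numeric: 1 + 2 + 1 + 1 + 1 + 1 + 1 + 3 = 11, so 50/11 = 4.5. This takes one rating score per model.

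**Are 50 positives reachable?** Assume 1,184 patients, 10% loss, event rates of 12% and 7%, and equal sites. Then 1,184 × 0.9 × (0.12 + 0.07)/2 × 3/4 = 75.9, so probably yes.

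**Simulation.** There were 100 charts and 2,000 runs per scenario (600 for Firth). Given outcome y, the rating is normal with mean βy and variance 1, so the true log odds ratio per SD is exactly β. Covariates have the SAP's structure and are unrelated to outcome. The true odds ratios, the complaint mix and site shares of 40/35/25% are assumptions. Overstatement = mean log OR / true log OR − 1; for example 0.861/0.693 − 1 = 24%.

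| Period | True OR (log) | Full model, mean log OR | Overstated by | 95% CI coverage | Rating only | Firth, full model |
|---|---|---|---|---|---|---|
| Factor | 1.5 (0.405) | 0.490 | 21% | 92% | 0.413 | 0.407 |
| Factor | 2 (0.693) | 0.861 | 24% | 91% | 0.717 | 0.710 |
| Factor | 3 (1.099) | 1.430 | 30% | 88% | 1.157 | 1.135 |
| Numeric | 1.5 (0.405) | 0.470 | 16% | 93% | 0.420 | 0.410 |
| Numeric | 2 (0.693) | 0.809 | 17% | 94% | 0.717 | 0.694 |
| Numeric | 3 (1.099) | 1.328 | 21% | 93% | 1.151 | 1.111 |

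On the odds-ratio scale with period as factor, true values of 1.5, 2 and 3 come out at about 1.63, 2.37 and 4.18 (exponentiated mean log OR). The rating-only model is off by about 2-5%, Firth on the full model by about 3% or less.

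**No association.** The full model has a mean log OR of 0.00 and rejects in 6.4% (factor) or 6.0% (numeric) of runs. The Monte Carlo standard error is √(0.05 × 0.95/2,000) = 0.5 percentage points, so the test is at most mildly liberal.

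**Power.** At true ORs of 1.5 and 2, with period as factor, the full model rejects in 50% and 90% of runs and the Wilcoxon test in 49% and 91%. Adjustment adds no evidence here.

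**Less favourable cases.** If one site supplies 80% of charts (80/13/7), about 5-6% of full-model fits fail or separate, and the Firth means with period as factor are 0.428, 0.716 and 1.142, which is 6%, 3% and 4% above the truth. With only 30 positives and 15 slopes there are 30/15 = 2.0 per slope, the overstatement at a true OR of 2 is 0.890/0.693 − 1 = 28%, and 3-4% of fits fail.

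**The case against.** The strongest reply is that this regression is supplementary. The Wilcoxon test is named first, does not depend on the covariate count and supplies every p value in Table 3. No decision rule rests on the adjusted odds ratio. All of this stands and limits the point to one reported estimate.

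A reader might infer that overfitting could make an invalid score look valid, or that the validation of the endpoint as a whole is inflated. Neither is supported. With no association the estimate is centred on zero, and the main comparison is untouched. A reader might also take 15 slopes as fixed, but section 13 a) does not settle the coding of period, so the count is 11 or 15. Larger overstatements can be produced by assuming a larger effect: at an odds ratio of 4.5 per SD the overstatement is 38% with 87% coverage. Nothing in the SAP supports an effect of that size.

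Adjustment is also defensible in itself. Ratings may differ by site or complaint, and group allocation could affect the item on documented differentials. Dropping every covariate is therefore a preference, not a correction. Finally, the sentence on covariates can be read as extending a rating-only model that is also to be fitted. The text does not settle this; if that is the intention, part of the fix is only to say so.

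What remains is that the adjusted estimate, as specified, is biased away from zero under either coding of period, and the section names no remedy.

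**Conclusion.** The point holds for the additional adjusted logistic model only. With 11 or 15 slopes and at most 50 positives, a non-null log odds ratio would be overstated by about 15-30%, with interval coverage of about 88-94%. These figures rest on true odds ratios of 1.5 to 3 per SD, a normally distributed rating and covariates unrelated to outcome. If covariates do predict the composite, part of any gap between the adjusted and rating-only odds ratios would be a genuine difference in what the two estimate, not bias. The Wilcoxon comparison, Table 3 as planned and the primary efficacy analysis are unaffected. This is a low-severity point that is cheap to correct.

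**What to change.** In section 13 a), do one of the following:
- fit the adjusted model with Firth penalised likelihood, keeping the covariates; or
- make the rating-only odds ratio the main estimate and show the adjusted one beside it.

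In either case list site once, state whether period is a factor or numeric, and define the rating score (which item or summary, and how the two raters are combined).

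Optionally, report from the same 100 reviews the proportion with a diagnostic error by item 13 among score-positive and score-negative patients, with exact confidence intervals. Sampling by score status makes these proportions directly estimable. A cut-off on the 7-point scale would have to be set in advance.

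The cost is a few lines of text and code and no further chart review. The downside is a slightly less standard estimator, or a less prominent case-mix adjustment, and a smaller reported odds ratio.

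### The covariate-adjusted validation model in SAP section 13 a) is too large for 100 charts: under ordinary maximum likelihood a true association would be overstated and its 95% interval would undercover

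*SAP*

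**What the plan says.** SAP section 13 a) draws the chart-review sample by score status: "Fifty patients with a diagnostic risk (positive primary endpoint) and 50 patients without a diagnostic risk (negative primary endpoint) will be randomly selected", from the three sites that share a record system. If there are too few positives, "the missing cases will be replaced with patients with a negative risk score", so 50 positives is a ceiling. The rating comes from the Safer Dx instrument: "For the selected 100 patients, two independent investigators will rate their agreement on a 7-point likert scale".

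Ratings are first compared between score-positive and score-negative charts by a Wilcoxon test. Then "logistic regression models will be performed with the primary endpoint composite score as dependent variable and the rating score as independent variable". The next sentence begins: "Additionally, following variables will be added as covariates: site, group allocation, period, site", and goes on to age, sex, complaint type and the Charlson index. Site appears twice. The section names no penalisation, covariate selection or small-sample correction for this model. Section 11 sets the general reporting convention: odds ratios with 95% confidence intervals and a two-sided 5% level.

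**The concern.** The chart review is there to show that the composite tracks diagnostic error; section 7.3 describes it as validating the primary outcome measure. The adjusted model repeats the fixed terms and baseline covariates of the primary efficacy model, but fits them to 100 charts instead of a trial planned at 1,184 patients. With few events per coefficient, maximum-likelihood logistic regression pushes non-zero log odds ratios away from zero and gives standard errors that are too small. Both errors favour the composite: if an association exists, the score looks more closely tied to diagnostic error than it is, and the estimate looks more precise than it is.

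**Working it through.** **Sample.** 50 + 50 = 100 charts. Choosing charts by the dependent variable does not itself bias logistic slopes, so what follows is a small-sample effect.

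**Slopes, from the SAP's own codings**

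| Term | Levels and source | Slopes |
|---|---|---|
| Rating | one score, 13 a) | 1 |
| Site | three sites, 13 a) | 2 |
| Group allocation | binary, 7.5.4 | 1 |
| Period | factor, six levels, as in 11.1 (or numeric, 7.5.4) | 5 (or 1) |
| Age, sex, Charlson index | 7.5.4 | 3 |
| Chief complaint | "0, fever 1, abdominal pain 2, syncope 3, non-specific complaint", 7.5.4 | 3 |

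Period as factor: 1 + 2 + 1 + 5 + 3 + 3 = 15, and 50/15 = 3.3 positives per slope. Period numeric: 15 − 4 = 11, and 50/11 = 4.5. The repeated site counts once.

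**Will 50 positives be reached?** The planned total is 74 × 4 periods × 4 clusters = 1,184. At 12% and 7% (the SAP's control rate and 5-point difference) the mean rate is 9.5%. With 10% loss, 1,184 × 0.095 × 0.9 = 101.2 positives. If the three sites contribute 50% to 90% of patients (an assumption), that gives 51 to 91. A shortfall is therefore not expected under the plan's own rates.

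**Simulation.** Samples of 50 positive and 50 negative charts were drawn from a simulated population with three sites and six periods, 2,500 to 8,000 data sets per row, and fitted with 15 slopes. The continuous-rating runs include assumed covariate effects. The 7-point runs use a skewed rating and no covariate effects. Odds ratios are per unit of rating; the bracketed estimate is the exponent of the mean log odds ratio.

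| Rating | True log OR (OR) | ML mean (OR) | ML coverage | Firth mean | Firth Wald coverage |
|---|---|---|---|---|---|
| Continuous | 0 (1.0) | 0.003 (1.00) | 93.4% | 0.002 | 96.6% |
| Continuous | 0.405 (1.5) | 0.506 (1.66) | 92.6% | 0.415 | 96.7% |
| Continuous | 0.693 (2.0) | 0.876 (2.40) | 91.7% | 0.710 | 97.1% |
| Continuous | 1.099 (3.0) | 1.420 (4.14) | 89.1% | 1.120 | 95.3% |
| 7-point | 0 (1.0) | 0.001 (1.00) | 93.3% | not run | not run |
| 7-point | 0.262 (1.3) | 0.325 (1.38) | 92.7% | 0.268 | 96.8% |
| 7-point | 0.405 (1.5) | 0.508 (1.66) | 90.6% | 0.415 | 96.4% |
| 7-point | 0.693 (2.0) | 0.911 (2.49) | 87.3% | 0.711 | 95.9% |

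- Inflation at a true OR of 2.0: 0.876/0.693 = 1.26 and 0.911/0.693 = 1.31. The median estimates are exp(0.847) = 2.33 and exp(0.874) = 2.40.
- Standard error at OR 2.0, continuous rating: the model gives 0.296 on average, against an actual SD of 0.340 (ratio 0.87).
- Rejection with no association: 6.6% and 6.7% (Wald), 7.4% and 7.8% (likelihood ratio). Separate runs with other assumed covariate distributions gave 6.5% to 8.0%.
- With 11 slopes: a true 0.693 gives mean 0.808 (OR 2.24), median exp(0.777) = 2.17, coverage 93.4%. On the 7-point rating a true 0.405 gives 0.475 (OR 1.61), coverage 93.3%. With no association, coverage is 94.2% to 94.7% and rejection 5.3% to 5.8% (Wald) or 5.8% to 6.7% (likelihood ratio).
- With only 30 positives and 15 slopes, 280 to 299 of 2,500 fits failed (11% to 12%), against about 1% or fewer with 50.

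**Is this small-sample bias or only the change of scale from adjustment?** In the 7-point runs the covariates have no effect, so the rating-only model targets the same odds ratio. It averages 0.723 for a true 0.693 (4% high), against 0.911 (31% high) with 15 slopes. Firth's method on the same 15 terms gives 0.711. The distortion comes from fitting too many terms by maximum likelihood.

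**The case against.** The strongest reply is that little rests on this odds ratio. The Wilcoxon comparison comes first, planned Table 3 (section 18.4) shows only ratings, Wilcoxon p-values and a rater kappa, no validity threshold is set on the odds ratio, and the analysis sits under Other Analyses. All of this stands and limits the weight of the point.

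Second, the plural in "logistic regression models will be performed with the primary endpoint composite score as dependent variable and the rating score as independent variable" followed by a separate sentence on covariates may mean an unadjusted model and then an adjusted one. That is a fair reading, but the text does not say so, and the adjusted model would still be distorted.

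Third, the count of 15 rests on treating period as a factor, which section 11.1 says only of the primary model. With a numeric period the error rate under no association is close to nominal, though a log odds ratio inflation of about 17% remains.

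Fourth, repeating the primary model's covariates is a defensible choice of consistency. This also stands. A reader might infer that site, period and condition should be removed. The SAP gives no ground for that, and a model cut to age and the Charlson index would lose sex and chief complaint while pairing age with an index that section 10.2 derives partly from age.

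**Conclusion.** The point holds for the adjusted odds ratio and its interval, on condition that the rating is truly associated with the composite. Then a true 2.0 is estimated at about 2.3 to 2.4 with 15 slopes and 2.2 with 11, and the nominal 95% interval covers about 87–93% or 93–95%. The lowest coverage belongs to an odds ratio of 2.0 per point on a 7-point scale, which is a strong association.

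A reader might infer that the model would make an invalid score look valid. The figures do not support that: with no association the odds ratio is centred on 1 and rejection is only modestly above 5% (about 6.5–8% with 15 slopes, 5–7% with 11). Nor does the point reach the Wilcoxon comparison, Table 3 or the primary efficacy result.

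The mechanism and the count are firm. The sizes rest on assumed covariate distributions and on a single rating per chart, whereas section 13 a) does not say how 13 items and two raters become one rating score. Fifty positives is the best case.

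**What to change.** In section 13 a), state that the logistic model with the rating alone is the main regression estimate. State that the covariate-adjusted model is fitted by Firth's penalised likelihood with profile-likelihood intervals, keeping the listed covariates and naming site once. It would help to say in the same sentence whether period is a factor or numeric.

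The cost is SAP wording only, and section 9.1 allows final changes before the efficacy analysis. The Firth Wald test is slightly conservative with no association (3.4% against 5%) and rejects less often otherwise: at a true OR of 1.5 with a continuous rating, 36.4% against 47.3% for maximum likelihood, part of which reflects the latter's inflation. Profile-likelihood intervals were not simulated; the Firth coverage figures are for Wald intervals. The rating-only model rejected in 4.4% to 5.2% of the runs with no adjusted association, but it estimates an unadjusted association, so the two estimates should be labelled as different quantities.
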